pre-post change in cognitive control or reward processing circuits as primary predictors, while controlling for baseline impulsivity and treatment group. The mediation effect is then estimated by taking the product of the estimates for **path a and b** and using the bootstrap method to obtain standard errors, confidence intervals, and the test for statistical significance.

To test whether treatment effects on cognitive control or reward processing circuits are specific in mediating improvements in impulsivity, we will explore whether treatment-related changes in other neural networks also mediate the effect of treatment on impulsivity. We will first screen these additional neural networks based on a significant effect of treatment on connectivity within these networks. Only networks that show significant change with treatment will be added to the multiple mediation analyses described above. The indirect effects of the cognitive control or reward processing circuits will be tested in the existence of the mediation effects of other neural networks using the bootstrapping method.

Power: Power for detecting the mediation effect depends on the size of the associations between (a) treatment group and changes in cognitive control and reward processing circuits, and (b) changes in cognitive control and reward processing circuits and changes in impulsivity. Based on tabulated recommendations for sample sizes needed to test mediation effects, with a sample size of $n=60$, we have more than 80% power to detect a significant mediation effect with medium effect size of both paths a and b.

Secondary Objective: ADHD patients with baseline MRI anomalies within reward processing circuits will respond to Vyvanse, but not Intuniv, treatment. Conversely, ADHD patients with baseline MRI anomalies that are circumscribed to cognitive control circuits (i.e., reward processing comparable to healthy controls) will predict response to either Intuniv or Vyvanse.

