We will test the moderation effect of the baseline MRI measures cognitive control and reward processing circuits on the treatment response. We will use linear regression models with pre-post change scores in impulsivity measures as outcomes and Group, baseline measures of cognitive control and reward processing circuits measured in predefined regions of interest (ROIs), and their interactions as predictors. Likelihood ratio tests will be used to test the effect of moderation with combination of multiple brain imaging measures.

Power: With sample size of $n=60$, the minimum detectable effect size of Cohen's f^2 is 0.09 (smaller than medium effect size 0.15) with 80% power for a two-sided test at the 5% significance level. If the effect size of interactions between baseline measures within cognitive control and reward processing circuits and Group is greater than f^2 is 0.09, we would be able to detect such effect size.

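### The SAP's minimum detectable f² of 0.09 for moderation is not attained at n=60: it is about 0.135 for one interaction and 0.17 to 0.22 for a joint test of two to four

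*SAP*

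**What the plan says.** The SAP's Secondary Objective asks whether baseline imaging of the cognitive control and reward circuits tells which children respond to which drug. The analysis is an ordinary linear model: "We will use linear regression models with pre-post change scores in impulsivity measures as outcomes", with "Group, baseline measures of cognitive control and reward processing circuits measured in predefined regions of interest (ROIs), and their interactions as predictors". For the joint question, "Likelihood ratio tests will be used to test the effect of moderation with combination of multiple brain imaging measures".

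The Power paragraph that follows reads "With sample size of $n=60$, the minimum detectable effect size of Cohen's f^2 is 0.09", at 80% power and a two-sided 5% level, and describes this as below the medium benchmark of 0.15. It then applies 0.09 to the "interactions between baseline measures within cognitive control and reward processing circuits and Group", in the plural.

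Neither document gives the number of ROIs, the number or type of interaction terms tested, the numerator degrees of freedom, or the reference distribution for the likelihood ratio statistic.

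On sample size, the protocol's Lay Summary speaks of 30 children with ADHD, randomized 1:1. Its Description of Subject Population requires 30 ADHD completers (80 to be enrolled) and, separately, 30 healthy control completers.

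**The concern.** A minimum detectable f² depends on n, the level, the power and the number of terms tested. The SAP gives the first three, and they do not lead to 0.09 for any number of terms. A reader of the Power paragraph would believe that the moderation analysis is well placed to find effects below medium size. If it is not, a null result could be read as evidence against moderation when the study had little chance of showing it.

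The missing count of terms makes this worse, because the detectable effect rises with each term in the joint test. The objective itself concerns a pattern across circuits ("baseline MRI anomalies that are circumscribed to cognitive control circuits"), so a single interaction is unlikely to be the whole test.

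The unstated reference distribution is a smaller matter. A likelihood ratio statistic is often referred to chi-square, which ignores the degrees of freedom spent on the regression and rejects too often in small samples.

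**Working it through.** **Inputs.** From the SAP, Secondary Objective: n = 60, two-sided 5%, 80% power, stated f² = 0.09, linear model with Group, ROI measures and interactions. Assumed: q ROIs, each with one Group-by-ROI interaction, q = 1 to 4. The model then has k = 2 + 2q coefficients including the intercept.

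**Step 1. Try to reproduce 0.09.** The normal approximation for one term is f² = (z_α + z_β)²/n.
- Two-sided: (1.960 + 0.842)²/60 = 7.85/60 = 0.131.
- One-sided: (1.645 + 0.842)²/60 = 6.18/60 = 0.103.

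The one-sided noncentral F value for one term is 0.106, with power of about 74% at 0.09. Even a one-sided test, which the SAP does not use, does not reach 0.09.

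**Step 2. Partial F test.** Power = P(F′(q, n−k, λ) > F crit), with λ = n·f². At f² = 0.09, λ = 60 × 0.09 = 5.4.

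| Terms q | k | F crit (q, 60−k) | Power at 0.09 | Minimum detectable f² | n needed for 0.09 |
|---|---|---|---|---|---|
| 1 | 4 | 4.013 | 63% | 0.135 | 90 |
| 2 | 6 | 3.168 | 51% | 0.170 | 111 |
| 3 | 8 | 2.783 | 44% | 0.196 | 126 |
| 4 | 10 | 2.557 | 39% | 0.219 | 138 |

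The other common convention, λ = (n−k)·f², is less favourable: 0.145, 0.189 and 0.262 for 1, 2 and 4 terms.

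**Step 3. Would a chi-square reference rescue 0.09?** In a normal linear model LR = n·ln(1 + qF/(n−k)). A test referred to chi-square therefore rejects when F > ((n−k)/q)·(exp(χ²₀.₉₅,q/n) − 1). Its true size is the F(q, n−k) tail beyond that cut-off.

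| Terms q | F cut-off implied | True size | Minimum detectable f² |
|---|---|---|---|
| 1 | 3.703 | 5.9% | 0.128 |
| 2 | 2.835 | 6.8% | 0.154 |
| 3 | 2.411 | 7.7% | 0.171 |
| 4 | 2.141 | 8.9% | 0.182 |

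So 0.09 is not attained under either reference. With two or more terms the detectable effect exceeds 0.15 under both. A simulation with 100,000 replicates, 30 per arm and normal errors gave sizes of 6.8% (2 terms) and 8.9% (4 terms) for the chi-square reference, against 5.0% and 4.9% for the F test.

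**Step 4. The protocol's 30 ADHD completers.** Group is the drug and the outcome is a pre-post change, so only treated children can enter the model. With n = 30 the Step 2 formula gives a minimum detectable f² of about 0.28 (1 term), 0.36 (2), 0.43 (3) and 0.50 (4). Power at 0.09 is about 35%, 26%, 21% and 18%.

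**The case against.** Four points deserve weight.

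**The number of terms is assumed.** This is true, and the upper end of four has no source in the documents. A combination of measures could even mean one composite score, hence one term. But one term is the most favourable case, and it gives 0.135, so the failure of 0.09 does not depend on the count. What does depend on it is the comparison with 0.15: for a single interaction the detectable effect is still below medium, and for two or more it is not.

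**A reader might infer that the SAP's joint test has an inflated false-positive rate.** The documents do not support that. They name no reference distribution, and in a linear model the likelihood ratio statistic is a monotone function of the partial F. With its exact null distribution it is the same test. The 6.8% to 8.9% figures hold only if chi-square is used, and should not be presented as an error in the plan.

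**The F test is exact only under normal, equal-variance errors.** In a simulated case with error SD = exp(0.4 × one ROI), the F test rejected 9.1% (2 ROIs) and 7.6% (4 ROIs), against 11.5% and 12.5% for chi-square. It was better, but not exact. Naming it also does nothing about the several impulsivity outcomes, for which no multiplicity rule is given.

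**The protocol plans to enrol 80 children with ADHD, so 60 completers is not impossible.** That stands, but the number the protocol says it needs is 30, and the SAP does not say where 60 comes from.

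**Conclusion.** The stated minimum detectable f² of 0.09 is wrong as written. At n = 60, 80% power and two-sided 5% it is about 0.135 for one interaction and about 0.17, 0.20 and 0.22 for joint tests of two, three and four. Power at 0.09 is about 63%, 51%, 44% and 39%. The claim of sensitivity below a medium effect fails for any joint test of two or more terms, under an F or a chi-square reference.

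This rests on λ = n·f², one Group-by-ROI interaction per ROI, and normal, equal-variance errors. It does not rest on any assumption about how the likelihood ratio test is calibrated. If only 30 treated children are analysed, every figure is less favourable.

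The unnamed reference distribution is a gap in specification and not a demonstrated inflation of error. The objective is secondary and no decision rule in the documents turns on this test, so the consequence is modest.

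**What to change.** **Power paragraph.** Replace 0.09 with the figure that matches the planned test, and state its numerator degrees of freedom. For example: *With 60 treated children with ADHD analysed, the minimum detectable f² at 80% power and two-sided 5% is 0.135 for a single Group-by-ROI interaction (1 numerator df), and 0.17, 0.20 or 0.22 for a joint test of 2, 3 or 4 interactions.* Drop the statement that the figure is below medium unless the test has one term. List the ROIs and the interaction terms, and give their number.

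**Sample size.** Reconcile 60 with the protocol's 30 ADHD completers, and recompute at the number that will be analysed.

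**Secondary safeguard.** Name the joint test: *The joint moderation effect will be tested by the partial F test comparing the linear models with and without the listed interaction terms.* If F was always intended, this only puts it on record.

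**Cost.** A few sentences and a list of terms, with no new data or software. The stated sensitivity becomes less favourable. Compared with a chi-square reference there would be fewer rejections: at n = 60 and f² = 0.15, 79% falls to 75% with two terms and 72% to 62% with four. That difference reflects the inflated size of the chi-square version.

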Children with Attention-Deficit/Hyperactivity Disorder (ADHD) are typically treated with two types of medications with differing mechanisms of action: stimulants and non-stimulants. The stimulant Vyvanse (lisdexamfetamine, LDX), and the non-stimulant Intuniv (extended-release guanficine, GXR), are both FDA-approved treatments for ADHD in children. Clinical trials have shown that both medications are effective in reducing ADHD symptoms, although the neurobiological mechanisms by which Vyvanse and Intuniv produce these effects remain unknown. The aim of this study is to examine the mechanisms by which LDX and GXR reduce symptoms in children with ADHD. MRI scanning will be used to understand the structure and blood flow within the brains of children with ADHD treated with LDX and GXR.

A total of thirty (30) children with ADHD and ten (10) age- and sex-matched, healthy controls will be scanned at the beginning of the study. In this first part of the study, MRI findings will be compared between the groups (i.e., children with and without ADHD) to see whether brain functioning of children with ADHD differs from that of healthy children. In the second part of the study, the children with ADHD will be randomized (1:1 ratio) to receive treatment with LDX or GXR for six (6) weeks. In the first few visits of the treatment phase of the study, the study doctor may adjust the medication dose to optimize its effect. At the end of the study, the children with ADHD treated with LDX or GXR will have a second MRI scan. The findings of that second MRI scan will be compared to the first MRI scan in order to identify brain changes due to the medication. These second MRI scans will also be compared to the scans of the healthy controls.

We seek to examine whether treatment with LDX and GXR leads to changes in brain structure and function and thereby help to reduce symptoms of ADHD. Furthermore, we will examine how these two drugs differ in yielding their therapeutic effect. This may inform how specific changes in the brain may underlie improvement in the various symptoms of ADHD.

Background, Significance and Rationale

Background, Significance and Rationale

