Exploratory Aim: To examine the concordance between the Pubertal Development Scale (Petersen et al., 1988) and the Tanner Stages and the acceptability of these measures to participants and their parents/guardians. Parent report will be collected if participants are <11 years, and self report will be collected if participants are 11 years or older.

Description of Subject Population

Sample #1

Specify subject population

Children with ADHD

Number of completers required to accomplish study aims

30

Projected number of subjects who will be enrolled to obtain required number of completers

80

Age range of subject population

6-17 years

Sample #2

Specify subject population

Healthy Control Children

Number of completers required to accomplish study aims

30

Projected number of subjects who will be enrolled to obtain required number of completers

80

Age range of subject population

6-17 years

Gender, Racial and Ethnic Breakdown

In terms of gender, we expect the majority of children with ADHD to be male (approximately 80%), which reflects the fact that ADHD is more common in boys than in girls.

In terms of ethnic breakdown, this sample will represent a wide array of racial and ethnic backgrounds that are representative of both the population in the Washington Heights area and New York City at large (e.g., 60% White, 40% Hispanic/Latino of any race, 20% Black/African American, 5% Asian, 10% other race, 5% two or more races). Additional efforts will be made to diversify the population of participants by advertising in community/neighborhood newspapers throughout New York City and surrounding areas. We will first seek IRB approval prior to releasing these advertisements.

Description of subject population

The subject populations will consist of:

- Children with ADHD
- Healthy control children, who will be matched on age and sex.

Recruitment Procedures

Describe settings where recruitment will occur

Study Recruitment Websites

Participants will be recruited through research study recruitment websites such as RecruitMe and Clinicaltrials.gov.

Flyers and Brochures

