- **For ADHD participants with a history of tic disorder:** Based on the information gathered from the medical history and the psychological assessments during the initial visit(s), the study doctor will carefully weigh the risks and the benefits of LDX treatment with the parent/guardian of the child participant. The decision to randomize the participant or to remove him/her from the study will depend on the study doctor's clinical judgment and the preferences of the parent/guardian. The study doctor will follow the same clinical practice guidelines for evaluating and treating co-occurring ADHD and tic disorder as doctors in the community. If the study doctor and parent/guardian agree that the benefits of potential treatment with LDX outweigh the risks, then the participant will proceed to the randomization procedures outlined below.
- **For female ADHD participants who have had their first period:** Female ADHD participants who have had their first period and who are sexually active will need to: (1) be using contraception prior to beginning treatment, and (2) agree to continue using contraception throughout the course of treatment in order to participate in the study. The study doctor will talk to female participants who have had their first period about ways to prevent pregnancy, the potential risks of the study medications on pregnancy (as part of consent/assent), as well as the limitations of urine pregnancy testing. Participants and their parents/guardians will be advised to notify the researcher immediately should they suspect that the participant is pregnant. If a participant is suspected to be pregnant, we will perform another pregnancy test to determine if she should continue the study. In case of pregnancy, the participant will discontinue the study early and we will provide assistance with obstetrical follow-up.

2. Randomization Procedures

Eligible ADHD participants will be randomized to treatment with LDX or GXR using a 1:1 ratio. Participants, research staff, and the study doctor will NOT be blinded to treatment.

3. Medication Management

Following randomization, participants will be taken through a medication management protocol over the subsequent 6 weeks. This protocol will begin with 4 weeks of medication titration, which will be followed by 2 weeks of medication maintenance. Titration will help the study doctor determine the minimum dose of medication necessary to achieve treatment response.

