- **Titration of GXR:** The treating physician will dose GXR to optimize clinical response. Titration will begin at 1 mg and will advance through the dosage range (1 - 4 mg) to find the best response that provides no more than mild adverse events. Treatment response will be defined as a clinician-rated CGI-I score ≤ 2 (Improved or Very Much Improved) with no more than mild associated adverse events based on a clinical review of side effects. For children under 25 kg/55 lbs, the dose of GXR will not exceed 1 mg per day. The treating clinician will monitor heart rate and blood pressure to ensure that cardiovascular risk is minimized. Flexibility in the dosing will be up to the treating physician as long as the dosing does not go outside of the FDA approved guidelines of 1 - 4 mg daily.

- **Concomitant Medication:** The treating physician will review any potential concomitant medications, and make recommendations as clinically indicated. For example, GXR doses may be adjusted when used concomitantly with strong CYP3A4 inhibitors (e.g., boceprevir, clarithromycin) or inducers (e.g., avasimibe, carbamazepine). In clinical practice, melatonin is often used to alleviate insomnia related to ADHD medications like LDX. The treating physician will have the option of recommending melatonin 1-6 mg nightly as needed for insomnia.

See Criteria for Early Discontinuation

Follow Up Evaluation and MRI Scan

After completing the medication trial, children with ADHD will be scheduled for a follow-up evaluation. The follow-up evaluation will be similar to the baseline evaluation but shorter in length. The second MRI scan will be identical to the first MRI scan.

1. **Neuropsychological Testing:** We will repeat all neuropsychological tests with the exception of the measure of intelligence, which is not expected to change during the study period.
2. **Diagnostic Assessments:** Likewise, we will repeat all diagnostic assessments with the exception of the diagnostic interview.

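### The SAP's minimum detectable f² of 0.09 at n=60 does not follow from its own inputs; a single interaction coefficient needs about 0.135 or more

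*SAP*

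**What the plan says.** The SAP's Secondary Objective regresses pre-post change in impulsivity on treatment group, baseline measures of the cognitive control and reward circuits in predefined regions of interest, and their interactions. For the combined imaging measures it adds: "Likelihood ratio tests will be used to test the effect of moderation with combination of multiple brain imaging measures".

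The Power paragraph under that objective takes n=60 and a 5% significance level and says: "the minimum detectable effect size of Cohen's f^2 is 0.09 (smaller than medium effect size 0.15) with 80% power for a two-sided test". The next sentence applies this value to the interactions between group and the baseline circuit measures, saying that if their effect size "is greater than f^2 is 0.09, we would be able to detect such effect size". The paragraph gives no formula, number of predictors or number of tested terms.

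On sample size, the protocol's Lay Summary says: "A total of thirty (30) children with ADHD and ten (10) age- and sex-matched, healthy controls will be scanned". In Description of Subject Population, Sample #1 (children with ADHD), the entry "Number of completers required to accomplish study aims" is 30, with 80 projected to enrol.

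**The concern.** Once an effect is expressed as Cohen's f², the sample size, significance level, power and number of tested terms almost fix the minimum detectable value; no standard deviation or allocation ratio is needed. The SAP supplies all of these except the number of tested terms, and one term is the most favourable choice. A value of 0.09 at n=60 looks too small even for one term.

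This is the only sensitivity figure given for the moderation objective, and it is used twice, the second time as a plain assurance of detection. If it is too optimistic, a null moderation result would be read as stronger evidence against moderation than the design can give.

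**Working it through.** **Inputs from the SAP (Secondary Objective, Power):** n=60; power 80%; two-sided α=0.05; effect measure f²; linear regression.

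**Assumptions, because the SAP does not state them:** the number of tested interaction terms u (1 as the most favourable case; 2 and 3 as scenarios) and the number of predictors p. With one baseline measure, p=3: group, baseline, interaction. With two measures p=5, and with three p=7.

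**Method.** For u added terms the F test has u and v = n − p − 1 degrees of freedom. Under the alternative it is noncentral F with λ = f² × n. Power = P{F′(u, v, λ) > F(0.95; u, v)}. The minimum detectable f² is the value that makes this 0.80. A second convention uses λ = f² × (u + v + 1).

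**Step 1: the plan's own figure.** u=1, p=3, so v = 60 − 3 − 1 = 56 and the critical F(1, 56) is 4.013. At f²=0.09, λ = 0.09 × 60 = 5.4 and power is 0.627. Under the second convention λ = 0.09 × 58 = 5.22 and power is 0.612. Neither is 0.80, so the figure is not reproduced.

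**Step 2: the value these inputs give.** Solving for 80% power at n=60, u=1:

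| Predictors | λ = f²·n | λ = f²·(u+v+1) |
|---|---|---|
| 1 | 0.1353 | 0.1353 |
| 3 | 0.1354 | 0.1401 |
| 5 | 0.1356 | 0.1453 |

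As a hand check, the large-sample approximation is (1.960 + 0.842)² / 60 = 7.849 / 60 = 0.131.

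**Step 3: the sample size that would support 0.09.** With λ = f²·n and p=3, n=89 gives power 0.799 and n=90 gives 0.803, so about 90 are needed. Under the second convention it is 92 (p=3) or 94 (p=5).

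**Step 4: can another reading give 0.09 at n=60?**

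| Reading | Detectable f² | Power at 0.09 |
|---|---|---|
| One-sided 5%, one coefficient | 0.106 | 74% |
| R² of 0.09 converted to f² (0.09/0.91) | 0.099 | – |
| Joint test of 2 interactions, p=5 | 0.170 | 51% |
| Joint test of 3 interactions, p=7 | 0.196 | 44% |

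None does. More tested terms or more predictors raise the value, so the missing detail cannot rescue it.

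**Step 5: a randomly varying baseline measure.** The calculation above treats the predictors as fixed. A simulation with 1:1 groups, one normally distributed baseline measure and its interaction with group (40,000 trials per point, n=60) gave power of 0.595 at f²=0.09, 0.760 at 0.135 and 0.802 at 0.15, with type I error 0.049. At f²=0.09, power was 0.798 at n=94 and 0.807 at n=96. On this basis 0.135 is itself slightly favourable. The normal distribution and single measure are assumptions, not from the documents.

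**Step 6: the sample size itself.** The outcome is a pre-post change compared between treatments. Under Randomization Procedures the protocol says "Eligible ADHD participants will be randomized to treatment with LDX or GXR using a 1:1 ratio", and under Follow Up Evaluation and MRI Scan, "After completing the medication trial, children with ADHD will be scheduled for a follow-up evaluation". Healthy controls have neither a treatment group nor a scheduled follow-up, so they cannot contribute to this n. For one coefficient (λ = f²·n, p=3):

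- n=30 (required ADHD completers): about 0.28.
- n=80 (all projected ADHD enrolees): about 0.10.

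**The case against.** Five points can be made for the plan.

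- **The qualitative message partly survives.** For one coefficient, 0.135 (or 0.140 to 0.145) is still below 0.15, and with λ = f²·n and 3 predictors power at f²=0.15 is 84%. This stands, with limits: the random-baseline simulation puts the value at about 0.15, and the joint-test scenarios exceed it.
- **Approximations give slightly less than 0.135.** The large-sample value is 0.131, and a 1-df likelihood ratio calculation gives 0.131 to 0.140. This also stands, but 0.131 is not 0.09.
- **The number may be mislabelled rather than miscalculated.** If 0.09 were an increment in R² and the full model explained about one third of the variance, f² would be 0.09/0.667 = 0.135. Nothing in the SAP supports that reading, and the sentence would still be wrong as written. It is a good reason to ask for the derivation before putting in a new number.
- **The n=60 question is separate.** That is right: 0.09 fails at n=60 itself. With 80 ADHD children projected to enrol, 60 analysed is possible, and the Lay Summary is weak evidence of the planned n because its 10 controls already differ from the 30 control completers required elsewhere. The n still has to be confirmed, because any restated figure depends on it.
- **The impact is limited.** This is a secondary objective, and the documents tie no stopping or sample-size decision to 0.09. That bears on priority, not on correctness.

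**Conclusion.** The concern holds. At n=60, 80% power and a two-sided 5% test, the minimum detectable f² for one interaction coefficient is about 0.135, not 0.09. The stated figure makes the detectable effect look one third smaller than the inputs allow ((0.135 − 0.09)/0.135 = 0.33). At f²=0.09 power is about 63%, a miss rate of about 37% (about 40% by simulation) against the 20% implied, and about 90 participants would be needed for 80% power (about 95 by simulation).

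Confidence is high that 0.09 does not follow from the stated inputs. It is moderate for the exact replacement, which lies between 0.135 and about 0.15 for one coefficient, depending on the noncentrality convention and on whether the baseline measure is treated as random. The joint-test values of about 0.17 and 0.20 are scenarios, because the SAP does not state the number of tested terms. How the SAP arrived at 0.09 is unknown. The point should be fixed, but it does not undermine the analysis itself.

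**What to change.** In the Power paragraph of the SAP's Secondary Objective:

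1. State the derivation: the test the figure refers to, the number of tested terms and predictors, and the noncentrality convention.
2. Replace 0.09 in both sentences with the value for that test at the n to be analysed. At n=60 this is about 0.135 for one interaction coefficient, about 0.17 for a joint 2-df test, or about 0.20 for 3 df.
3. Keep the comparison with a medium effect of 0.15 only if the figure is for a single coefficient and the restated value is below 0.15.
4. Reword the second sentence so that it speaks of 80% power at the restated value and does not promise detection.
5. Confirm that 60 is the number of randomised ADHD participants to be analysed, and reconcile it with the protocol's Lay Summary and Sample #1 entry. If the number is 30, the single-coefficient value is about 0.28.

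The cost is SAP wording only. No analysis, endpoint or participant procedure changes; the stated sensitivity becomes less favourable.
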